6.1.2. Medical Devices

The combination products used in the study are tirzepatide investigational SDP and placebo SDP.

6.2. Preparation, Handling, Storage, and Accountability

- The investigator or designee must confirm appropriate storage conditions have been maintained during transit for all study intervention received and any discrepancies are reported and resolved before use of the study intervention.
- Only participants enrolled in the study may receive study intervention. Only authorized study personnel may supply, prepare, or administer study intervention.
- All study intervention must be stored in a secure, environmentally controlled, and monitored (manual or automated) area in accordance with the labeled storage conditions with access limited to the investigator and authorized study personnel.

- The investigator or authorized study personnel are responsible for study intervention accountability, reconciliation, and record maintenance (that is, receipt, reconciliation, and final disposition records).
- Further guidance and information for the final disposition of unused study interventions are provided in the Study Reference Manual.

6.3. Assignment to Study Intervention

Participants who meet all criteria for enrollment will be randomized to 1 of the study treatment groups at Visit 3. Assignment to treatment groups will be determined by a computer generated random sequence using an Interactive Web Response System (IWRS). Participants will be randomized in a **CCI** ratio to receive tirzepatide 5 mg, 10 mg, 15 mg, or placebo.

6.4. Blinding

This study is designed as a randomized, double-blind study to minimize bias. Assignment to treatment groups will be determined by a computer-generated random sequence using the IWRS. Investigators, site staff, clinical monitors, and participants will remain blinded to the treatment assignments until the study is complete.

Emergency unblinding for AEs may be performed through the IWRS, which may supplement or take the place of emergency codes generated by a computer drug-labeling system. This option may be used ONLY if the participant's well-being requires knowledge of the participant's treatment assignment. All actions resulting in an unblinding event are recorded and reported by the IWRS.

In case of an emergency, the investigator has the sole responsibility for determining if unblinding of a participant's treatment assignment is warranted for medical management of the event. The participant's safety must always be the first consideration in making such a determination. If a participant's treatment assignment is unblinded, Lilly must be notified immediately. If the investigator decides that unblinding is warranted, it is the responsibility of the investigator to promptly document the decision and rationale and notify Lilly as soon as possible.

If an investigator, site personnel performing assessments, or participant is unblinded, the participant must be discontinued from the study. In cases where there are ethical reasons to have the participant remain in the study, the investigator must obtain specific approval from a sponsor clinical research physician (CRP) for the participant to continue in the study.

6.5. Study Intervention Compliance

Study intervention compliance will be determined by the following:

- Study intervention administration data will be recorded by the participant and reviewed by the investigator at each study visit.
- The participants will be instructed to return any unused study intervention and/or empty cartons at the next visit to the study site for the purpose of performing drug accountability.

In the 3 tirzepatide treatment groups, as well as the placebo group, treatment compliance for each visit interval is defined as taking at least **CCI** of the required doses of study intervention.

Similarly, a participant will be considered significantly noncompliant if he or she is judged by the investigator to have intentionally or repeatedly taken more than the prescribed amount of medication.

In addition to the assessment of a participant's compliance with the study intervention administration, other aspects of compliance with the study treatments will be assessed at each visit based on the participant's adherence to the visit schedule, completion of study diaries, the results of home BG monitoring, and any other parameters the investigator considers necessary.

Participants considered to be poorly compliant with their medication and/or the study procedures will receive additional training and instruction, as required, and will be reminded of the importance of complying with the protocol.

6.6. Dose Modification

6.6.1. Tirzepatide

Please refer to Section 6.1.1 for tirzepatide administration. Study intervention dose modification is not permitted except for management of intolerable gastrointestinal symptoms.

Management of Participants with Gastrointestinal Symptoms

In participants who experience intolerable gastrointestinal symptoms (for example, nausea, vomiting, or diarrhea) at any time during the study, the following measures are recommended:

1. counseling on dietary behaviors that may help mitigate nausea and vomiting, (for example, eating smaller meals, splitting 3 daily meals into 4 or more smaller ones, and stopping eating when they feel full).
2. if symptoms persist despite #1, prescribing symptomatic medication (for example, antiemetic or antidiarrheal medication), at the investigator's discretion.
3. if symptoms persist despite #1 and #2, temporarily interrupting study intervention (omit 1 dose, the participant will take 3 of 4 doses at that dose level). Study intervention should be resumed at the assigned dose immediately, either alone or in combination with symptomatic medication, which can also be utilized to manage symptoms.

If intolerable gastrointestinal symptoms (for example, nausea, vomiting, or diarrhea) persist despite the above measures before or at Visit 5 (the scheduled visit in Week 8), the participant should discontinue the study intervention.

If intolerable gastrointestinal symptoms (for example, nausea, vomiting, or diarrhea) persist despite the above measures after Visit 5 (the scheduled visit in Week 8) the investigator should contact Lilly to consider continuing treatment at a lower maintenance dose of study intervention in a blinded fashion, for example:

- Participants at 5 mg will decrease the dose to placebo.
- Participants at 7.5 mg or 10 mg will decrease the dose to 5 mg.
- Participants at 12.5 mg or 15 mg will decrease the dose to 10mg.

If de-escalation of the tirzepatide dose is necessary, the investigator will use the IWRS to receive the appropriate tirzepatide dispensing information. If de-escalation is needed between scheduled visits, the IWRS will have unscheduled visits dedicated to providing dispensing information for

participants whose dose has been de-escalated. Those participants who have their dose de-escalated, will not be escalated again. The dose can be de-escalated only once and should before Week 24 (after Week 24, dose decreases will not be allowed). After that, the participants will have to discontinue study intervention if intolerable gastrointestinal AE persists and stay in the study.

6.7. Continued Access to Study Intervention after the End of the Study

Study completion will occur after all participants complete the follow up visit. Investigators will continue to follow SoA (Section 1.3) for all participants until notified by Lilly that study completion has occurred.

Tirzepatide will not be made available after conclusion of the study to participants.

6.8. Treatment of Overdose

Overdose was defined as administration of more than a total of 15 mg of tirzepatide in less than a 72-hour period (Note: to preserve blinding of the study intervention, administration of study intervention more than 1 injection in less than 72 hours will be reported as an AE for further evaluation).

In the event of overdose, the investigator should:

- Contact the medical monitor immediately.
- Evaluate the participant to determine, in consultation with the medical monitor, whether study intervention should be interrupted, and reinstitute when the investigator believes it is safe to do so (see section 7.1.2 for reinstitution based on number of doses missed).
- Closely monitor the participant for any AE/SAE and laboratory abnormalities as medically appropriate until, for example, study intervention no longer has a clinical effect or can no longer be detected systemically (at least 30 days).
- Appropriate supportive treatment should be initiated according to the participant's clinical signs and symptoms.

6.9. Concomitant Therapy

Participants will be permitted to use concomitant medications that they require during the study, except certain medications that may interfere with the assessment of efficacy and safety characteristics of the study treatments, such as GLP-1 receptor agonists, dipeptidyl peptidase-4 inhibitors, pramlintide, drugs with approved weight loss indication and systemic glucocorticoid therapy >14 days.

Investigative site staff will inform participants that they must consult with the investigator or a designated site staff member upon being prescribed any new medications during the study. This may not be possible when initiated for treatment of medical emergencies, in which case, the participant will inform the investigator or a designated site staff member as soon as possible.

Any nonstudy medications that the participant is receiving at the time of enrollment or receives during the study must be recorded on the CRF along with:

- Reason for use

- Dates of administration including start and end dates
- Dosage information including dose and frequency for concomitant therapy of special interest.

Nonstudy medications taken by participants who are screened but not randomized will not be reported to Lilly unless an SAE or AE occurs that the investigator believes may have been caused by a study procedure.

6.9.1. Initiation of New Antihyperglycemic Medication

The introduction of new antihyperglycemic medication is expected during the study only in the following situations:

- As an antihyperglycemic intervention for severe, persistent hyperglycemia (“rescue therapy”), as defined in Section 6.9.1.1
- In those participants who require permanent discontinuation of study intervention, but remain in the study (Section 7.1)
- During the safety follow-up period (between Visit 11 [Week 40] or ET and Visit 801).
- Short-term insulin use for up to 14 days is allowed for certain clinical situations (for example, acute illness, hospitalization, or elective surgery). This insulin use must be differentiated from insulin use as rescue therapy when reported in the CRF.

The choice of new antihyperglycemic medication will be at the discretion of the investigator and follow clinical guidelines. Glucagon-like peptide-1 receptor agonists, dipeptidyl peptidase-4 inhibitors, and pramlintide are not allowed at any time during the study.

6.9.1.1. Rescue Therapy

If a participant develops severe, persistent hyperglycemia after randomization, a new antihyperglycemic medication (“rescue therapy”) may be medically indicated after investigator assessment.

Investigators will be trained on the application of criteria for deciding when and how to intervene with participants who do not reach glycemic targets. If met the following prespecified severe, persistent hyperglycemia criteria and no intercurrent cause of the hyperglycemia could be identified (investigators should first confirm that the participant is fully compliant with the assigned therapeutic regimen and that he or she does not have an acute condition causing severe hyperglycemia), rescue medication will be prescribed as an add-on to randomized treatment. Participants will continue in the trial until they complete all study visits.

Severe, Persistent Hyperglycemia

- If any of the FBG values within 1 week for 2 consecutive weeks,
 - $>270 \text{ mg/dL} (>15.0 \text{ mmol/L})$ from baseline to end of Week 5, or
 - $>240 \text{ mg/dL} (>13.3 \text{ mmol/L})$ from Week 6 to end of Week 11, or
 - $>200 \text{ mg/dL} (>11.1 \text{ mmol/L})$ from Week 12 to end of trial, or
 - $\text{HbA1c} \geq 8.5\% (\geq 69 \text{ mmol/mol})$ by and after Week 24

The date and time of rescue medication administration as well as the name and dosage regimen of the rescue medication must be recorded.

7. Discontinuation of Study Intervention and Participant Discontinuation/Withdrawal

Discontinuation of specific sites or of the study as a whole are handled as part of Section 10.1 Appendix 1.

7.1. Discontinuation of Study Intervention

When necessary, a participant may be permanently discontinued from study intervention. If so, the participant will discontinue the study intervention, could receive another glucose-lowering intervention and will remain in the study and follow procedures for all remaining study visits, as shown in the SoA. The new glucose-lowering intervention will be recorded on the CRF specified for collecting antihyperglycemic medications.

A participant should be permanently discontinued from study intervention if

- the participant becomes pregnant during the study (will also be withdrawn from the study)
- the participant is diagnosed with T1DM (will also be withdrawn from the study)
- the participant discontinues due to a hepatic event or liver test abnormality (see section 7.1.1)
- the participant requests to discontinue study intervention.
- the participant is diagnosed with an acute or chronic pancreatitis
- the participant is diagnosed with MTC after randomization, or has post randomization calcitonin value ≥ 35 ng/L that has increased at least 50% over baseline
- the participant is diagnosed with an active or untreated malignancy (other than basal or squamous cell skin cancer, in situ carcinomas of the cervix, or in situ prostate cancer) after randomization
- the participant has any significant study intervention related hypersensitivity reaction
- the participant has any other TEAE, SAE, or clinically significant laboratory value for which the investigator believes that permanent study intervention discontinuation is the appropriate measure to be taken.

7.1.1. Liver Chemistry Stopping Criteria

Discontinuation due to a hepatic event or liver test abnormality

Participants who are discontinued from study intervention due to a hepatic event or liver test abnormality should have additional hepatic safety data collected via CRF.

The study intervention should be **interrupted** and close hepatic monitoring initiated (Section 10.5) if one or more of these conditions occur:

| Elevation | Exception |
|---|--|
| ALT or AST $>8 \times$ ULN | |
| ALT or AST $>5 \times$ ULN for more than 2 weeks | |
| ALT or AST $>3 \times$ ULN and either TBL $>2 \times$ ULN or INR >1.5 | For participants with Gilbert's syndrome: If baseline direct bilirubin is >0.5 mg/dL, then doubling of direct bilirubin should be used for drug interruption decisions rather than TBL $>2 \times$ ULN. |

| | |
|---|---|
| ALT or AST $>3 \times$ ULN with the appearance of fatigue, nausea, vomiting, right upper quadrant pain or tenderness, fever, rash, and/or eosinophilia ($>5\%$) | |
| ALP $>3 \times$ ULN, when the source of increased ALP is the liver | |
| ALP $>2.5 \times$ ULN and TBL $>2 \times$ ULN | For participants with Gilbert's syndrome: If baseline direct bilirubin is >0.5 mg/dL then doubling of direct bilirubin should be used for drug interruption decisions rather than TBL $>2 \times$ ULN. |
| ALP $>2.5 \times$ ULN with the appearance of fatigue, nausea, vomiting, right upper quadrant pain or tenderness, fever, rash, and/or eosinophilia ($>5\%$) | |

Source: FDA Guidance for Industry: Drug-Induced Liver Injury: Premarketing Clinical Evaluation, July 2009 and other consensus guidelines, with minor modifications

Abbreviations: ALT = alanine aminotransferase; AST = aspartate aminotransferase; ALP = alkaline phosphatase; INR = international normalized ratio; TBL = total bilirubin; ULN = upper limit of normal.

Resuming study intervention after elevated liver tests

Resumption of the study intervention can be considered only in consultation with the Lilly-designated medical monitor and only if the liver test results return to baseline and if a self-limited non-drug etiology is identified. Otherwise, the study intervention should be discontinued.

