8.2.7.1. Hepatic Safety Monitoring

Close hepatic monitoring

Initiating laboratory and clinical monitoring for abnormal liver laboratory test results

Laboratory tests, including ALT, AST, ALP, TBL, direct bilirubin (D. Bil), gamma-glutamyltransferase (GGT), and creatine kinase (CK), should be repeated within 48 to 72 hours to confirm the abnormality and to determine if it is increasing or decreasing, if one or more of these conditions occur:

| | |
|--|--|
| If a participant with baseline results of... | develops the following elevations: |
| ALT or AST $<1.5 \times$ ULN | ALT or AST $\geq 3 \times$ ULN |
| ALP $<1.5 \times$ ULN | ALP $\geq 2 \times$ ULN |
| TBL $<1.5 \times$ ULN | TBL $\geq 2 \times$ ULN (except for patients with Gilbert's syndrome) |
| ALT or AST $\geq 1.5 \times$ ULN | ALT or AST $\geq 2 \times$ baseline |
| ALP $\geq 1.5 \times$ ULN | ALP $\geq 2 \times$ baseline |
| TBL $\geq 1.5 \times$ ULN | TBL $\geq 1.5 \times$ baseline (except for patients with Gilbert's syndrome) |

Abbreviations: ALP = alkaline phosphatase; ALT = alanine aminotransferase; AST = aspartate aminotransferase; TBL = total bilirubin; ULN = upper limit of normal.

What to do if the abnormal condition persists or worsens

If the abnormality persists or worsens, clinical and laboratory monitoring, and evaluation for possible causes of abnormal liver tests should be initiated by the investigator in consultation with the Lilly-designated medical monitor. At a minimum, this evaluation should include physical examination and a thorough medical history, including symptoms, recent illnesses (for example, heart failure, systemic infection, hypotension, or seizures), recent travel, history of concomitant medications (including OTC), herbal and dietary supplements, history of alcohol drinking and other substance abuse.

Frequency of monitoring

Initially, monitoring of symptoms and hepatic biochemical tests should be done at a frequency of 1 to 3 times weekly, based on the participant's clinical condition and hepatic biochemical tests.

Subsequently, the frequency of monitoring may be lowered to once every 1 to 2 weeks, if the participant's clinical condition and lab results stabilize.

Monitoring of ALT, AST, ALP, and TBL should continue until levels normalize or return to approximate baseline levels.

Comprehensive hepatic evaluation

When to perform a comprehensive evaluation

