A comprehensive evaluation (Section 10.5 Appendix 5) should be performed to search for possible causes of liver injury if one or more of these conditions occur:

| If a participant with baseline results of... | develops the following elevations: |
|--|---|
| ALT or AST $<1.5 \times$ ULN | ALT or AST $\geq 3 \times$ ULN with hepatic signs/symptoms ^a , or ALT or AST $\geq 5 \times$ ULN |
| ALP $<1.5 \times$ ULN | ALP $\geq 3 \times$ ULN |
| TBL $<1.5 \times$ ULN | TBL $\geq 2 \times$ ULN (except for patients with Gilbert's syndrome) |
| ALT or AST $\geq 1.5 \times$ ULN | ALT or AST $\geq 2 \times$ baseline with hepatic signs/symptoms ^a , or ALT or AST $\geq 3 \times$ baseline |
| ALP $\geq 1.5 \times$ ULN | ALP $\geq 2 \times$ baseline |
| TBL $\geq 1.5 \times$ ULN | TBL $\geq 2 \times$ baseline (except for patients with Gilbert's syndrome) |

Abbreviations: ALP = alkaline phosphatase; ALT = alanine aminotransferase; AST = aspartate aminotransferase; TBL = total bilirubin level; ULN = upper limit of normal.

^a Hepatic signs/symptoms are severe fatigue, nausea, vomiting, right upper quadrant abdominal pain, fever, rash, and/or eosinophilia $>5\%$.

What a comprehensive evaluation should include

At a minimum, this evaluation should include physical examination and a thorough medical history, as outlined above, as well as tests for PT-INR; tests for viral hepatitis A, B, C, or E; tests for autoimmune hepatitis; and an abdominal imaging study (for example, ultrasound or computed tomography [CT] scan).

Based on the patient's history and initial results, further testing should be considered in consultation with the Lilly-designated medical monitor, including tests for hepatitis D virus, cytomegalovirus, Epstein-Barr virus, acetaminophen levels, acetaminophen protein adducts, urine toxicology screen, Wilson's disease, blood alcohol levels, urinary ethyl glucuronide, and blood phosphatidylethanol. Based on the circumstances and the investigator's assessment of the participant's clinical condition, the investigator should consider referring the participant for a hepatologist or gastroenterologist consultation, magnetic resonance cholangiopancreatography, endoscopic retrograde cholangiopancreatography, cardiac echocardiogram, or a liver biopsy.

Additional hepatic data collection (hepatic safety CRF) in study participants who have abnormal liver tests during the study

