Additional hepatic safety data collection in hepatic safety CRF should be performed in study participants who meet 1 or more of the following 5 conditions:

1. Elevation of serum ALT to $\geq 5 \times$ ULN on 2 or more consecutive blood tests (if baseline ALT $<1.5 \times$ ULN)
 - In participants with baseline ALT $\geq 1.5 \times$ ULN, the threshold is ALT $\geq 3 \times$ baseline on 2 or more consecutive tests
2. Elevated TBL to $\geq 2 \times$ ULN (if baseline TBL $<1.5 \times$ ULN) (except for cases of known Gilbert's syndrome)
 - In participants with baseline TBL $\geq 1.5 \times$ ULN, the threshold should be TBL $\geq 2 \times$ baseline
3. Elevation of serum ALP to $\geq 2 \times$ ULN on 2 or more consecutive blood tests (if baseline ALP $<1.5 \times$ ULN)
 - In participants with baseline ALP $\geq 1.5 \times$ ULN, the threshold is ALP $\geq 2 \times$ baseline on 2 or more consecutive blood tests
4. Hepatic event considered to be a SAE

5. Discontinuation of study intervention due to a hepatic event

Note: the interval between the two consecutive blood tests should be at least 2 days.

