8.3.4.10. Hepatobiliary Disorders

All events of treatment emergent biliary colic, cholecystitis, or other suspected events related to gallbladder disease should be evaluated and additional diagnostic tests performed, as needed. In cases of elevated liver markers, hepatic monitoring should be initiated as outlined in Section 8.2.7.1 and Section 10.5 Appendix 5.

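### For participants enrolled with ALT or AST above 2.5 and below 3.0 × ULN, the 48–72 h repeat trigger lies above the 5 × ULN level of a drug-interruption rule

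*Protocol*

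**What the plan says.** **Eligibility.** Protocol 5.2, exclusion [15], removes ALT or AST of 3.0 × ULN or more at Visit 1. Its note expressly admits participants with non-alcoholic fatty liver disease whose ALT is below 3.0 × ULN. Under footnote p of the Schedule of Activities (1.3), the screening chemistry value is the baseline.

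**Repeat trigger.** The close-monitoring part of 8.2.7.1 says that liver tests "should be repeated within 48 to 72 hours to confirm the abnormality" when a threshold is crossed. If baseline is "ALT or AST $<1.5 \times$ ULN", the threshold is 3 × ULN. If baseline is 1.5 × ULN or more, it is "ALT or AST $\geq 2 \times$ baseline". If the abnormality persists, "Initially, monitoring of symptoms and hepatic biochemical tests should be done at a frequency of 1 to 3 times weekly".

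**Interruption rule.** 7.1.1 lists fixed multiples of ULN that do not depend on baseline. One of them is "ALT or AST $>5 \times$ ULN for more than 2 weeks".

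**Later steps for a raised baseline.** Without symptoms, the comprehensive evaluation starts at "ALT or AST $\geq 3 \times$ baseline". The ALT threshold for the hepatic safety CRF is also three times baseline, worded as "baseline on 2 or more consecutive tests".

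**The concern.** An alert should come no later than the stopping level it supports. Here the alert scales with baseline and the interruption rule does not, so at a high enough baseline their order reverses. It reverses only for the participants admitted with the highest liver enzymes. For everyone else, a value above 5 × ULN has already triggered the 48–72 h repeat.

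The rule also depends on duration, so it cannot be applied without a second measurement. After baseline, the chemistry panel is scheduled only at Visits 6, 9 and 11, at early termination and at Visit 801. Visit 9 is Week 24 and Visit 11 is Week 40. A value in the gap at Week 24 has no further scheduled chemistry for 40 − 24 = 16 weeks, while weekly dosing continues. What is missing is a timed retest, not any possibility of a retest.

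**Working it through.** The plan states no figure on this point, so there is none to reproduce. The check is threshold arithmetic.

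**Inputs.** Eligible baseline b < 3.0 × ULN (5.2 [15]). Repeat trigger 2b for b ≥ 1.5 × ULN, and asymptomatic evaluation level 3b (both 8.2.7.1). Interruption level 5 × ULN (7.1.1).

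**Where the order reverses.** 2b > 5 exactly when b > 2.5. With the eligibility limit, the affected range is 2.5 < b < 3.0 × ULN.

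| Baseline b (× ULN) | Repeat trigger 2b | Uncovered width, max(0, 2b − 5) | Rise needed to reach 5 × ULN, 5/b − 1 | Asymptomatic evaluation 3b | Trigger with cap, min(2b, 5) |
|---|---|---|---|---|---|
| 1.5 | 3.0 | 0 | – | 4.5 | 3.0 |
| 2.0 | 4.0 | 0 | – | 6.0 | 4.0 |
| 2.5 | 5.0 | 0 | – | 7.5 | 5.0 |
| 2.6 | 5.2 | 0.2 | 92% | 7.8 | 5.0 |
| 2.7 | 5.4 | 0.4 | 85% | 8.1 | 5.0 |
| 2.8 | 5.6 | 0.6 | 79% | 8.4 | 5.0 |
| 2.9 | 5.8 | 0.8 | 72% | 8.7 | 5.0 |

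The width approaches, but never reaches, 1.0 × ULN as b approaches 3.0.

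**Two readings of the table.** Read enzyme by enzyme, the gap exists whatever the other enzyme's baseline. The first row, however, says "ALT or AST $<1.5 \times$ ULN". A participant with one enzyme below 1.5 × ULN could be read into that row and would then be repeated at 3 × ULN, which closes the gap. On this narrowest reading, the gap needs both enzymes at or above 1.5 × ULN.

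**An example that escapes on either reading.** Baseline ALT is 2.8 and AST 1.6 × ULN, so the triggers are 5.6 and 3.2. Later values are ALT 5.3 and AST 3.0 × ULN. The ratios are 5.3/2.8 = 1.89 and 3.0/1.6 = 1.88, both below 2, so no repeat is required; yet ALT is above 5 × ULN. The other enzyme's own trigger can be lower and may be crossed first; in this example it is not.

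**Other text that might close the gap.**
- 8.2.5 asks for repeats of clinically significant abnormal values. This rests on the investigator's judgment and sets no interval.
- 8.3.4.10 says "In cases of elevated liver markers, hepatic monitoring should be initiated as outlined in Section 8.2.7.1", which refers back without adding a threshold. Appendix 5 (10.5) also refers back to 8.2.7.1.
- The monitoring clause in 7.1.1 applies only once one of its criteria is met.

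**Expected number.** The documents give no rate. Assume that 0.5–2% of 200 participants enrol above 2.5 × ULN (1 to 4 participants) and that 5–20% of these have a value in the band.
- Low: 200 × 0.005 × 0.05 = 0.05
- High: 200 × 0.02 × 0.20 = 0.8

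**The case against.** The two provisions do different jobs: one is a repeat trigger relative to baseline, the other an interruption rule qualified by duration. Scaling alerts to a raised baseline is defensible, and nothing in the documents requires a repeat trigger to sit below every interruption level. A site applying the two-week clause would have to retest anyway.

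Other safeguards also remain. A single value above 8 × ULN interrupts drug, and so does a value above 3 × ULN with symptoms, with bilirubin above 2 × ULN or with INR above 1.5. Section 7.1 lets the investigator stop drug for any clinically significant laboratory value, and many investigators would retest under 8.2.5. Scheduled chemistry while drug is still being dispensed falls only at Visits 6 and 9, so few scheduled values could land in the band. Finally, changing the table needs a protocol amendment with ethics approval (10.1.1), and health authority approval if it is substantial.

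Most of this stands as a limit on size. The case left uncovered is an isolated, asymptomatic value in a narrow band, and it will be rare. It does not remove the gap. The retest implied by the duration clause is not written as an instruction and has no date. A site could reasonably take the 2 × baseline row to mean that no timed repeat is due. The sparse schedule makes an event less likely to be seen but lengthens the wait after one. The approval burden is real but can be shared with another amendment.

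**Conclusion.** The concern holds. For baseline ALT or AST above 2.5 and below 3.0 × ULN, the 48–72 h repeat trigger exceeds the 5 × ULN level in 7.1.1, by less than 1.0 × ULN. This follows from the documents' own thresholds and needs no outside figure. On the narrowest reading of the table it applies only when both enzymes were at or above 1.5 × ULN at baseline.

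The likely number affected is none or one (0.05 to 0.8 expected), and lower still on the narrowest reading. That estimate rests entirely on the two assumed percentages. Efficacy endpoints, analyses and sample size are untouched. It is a small safety inconsistency that should be corrected because the correction is cheap.

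**What to change.** In the close-monitoring table of 8.2.7.1, change the ALT/AST row for baseline ≥1.5 × ULN to read: ALT or AST ≥2 × baseline or >5 × ULN, whichever is lower. The uncovered width then becomes 0 at every eligible baseline. The existing 48–72 h repeat and, if the value persists, the existing monitoring of 1 to 3 times weekly would then apply, so no separate two-week recheck is needed. The 7.1.1 thresholds and the ALP and bilirubin rows stay as they are.

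The cost is one table row, a site notice and the usual amendment approvals, which can be bundled with another change. Per affected participant it adds about 1 + 2 weeks × (1 to 3 per week) = 3 to 7 liver panels over the first two weeks.
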